8.3.3 Guidance for all other adverse reactions

Consider performing an analysis of serum potassium, calcium, phosphorous, and magnesium for all adverse reactions, if indicated. If electrolyte values are outside of the normal range, interrupt ribociclib administration, correct electrolytes with supplements or appropriate therapy as soon as possible, and repeat electrolyte testing until documented normalization of the electrolytes.

Patients who experience renal impairment (not due to other contributing factors) of grade 2 or higher during the treatment period should discontinue treatment and should be followed for safety assessments.

For all other adverse events please follow recommendations in Table 22.

Grade	Ribociclib dose adjustment and management recommendation
1	No dose adjustment recommended. Initiate appropriate medical therapy and monitor.
2	Dose interruption until recovery to grade ≤ 1 . Initiate appropriate medical therapy and monitor. Re-initiate ribociclib at the same dose. If the same toxicity recurs at grade 2, interrupt ribociclib until recovery to grade ≤ 1 . Re-initiate ribociclib at the next lower dose level.
3	Dose interruption until recovery to grade ≤ 1 . Initiate appropriate medical therapy and monitor. Re-initiate ribociclib at the next lower dose level. If toxicity recurs at grade 2: temporary dose interruption until recovery to grade ≤ 1 and reduce ribociclib dose the next lower dose level. If toxicity recurs at grade 3, discontinue ribociclib.
4	Discontinue ribociclib and treat with appropriate medical therapy.

Table 23: Ribociclib dose adjustment and management recommendation for all other adverse reactions

8.3.3.1 Management of specific toxicities

Additional follow-up for hepatic toxicities

Increase in transaminases combined with total bilirubin (TBIL) increase may be indicative of drug-induced liver injury (DILI), and should be considered as clinically important events.

The threshold for potential DILI may depend on the patient's baseline AST/ALT and TBIL value; patients meeting any of the following criteria will require further follow-up as outlined below:

- For patients with normal ALT und AST and TBIL value at baseline: AST or ALT $> 3.0 \times$ ULN combined with TBIL $> 2.0 \times$ ULN
- For patients with elevated AST or ALT or TBIL value at baseline: (AST or ALT $> 2 \times$ baseline AND $> 3.0 \times$ ULN) OR (AST or ALT $> 8.0 \times$ ULN), whichever is lower combined with (TBIL $> 2 \times$ baseline AND $> 2.0 \times$ ULN)

Medical review needs to ensure that liver test elevations are not caused by cholestasis, defined as: ALP elevation $> 2.0 \times$ ULN with R value < 2 in patients without bone metastasis, or elevation of ALP liver fraction in patients with bone metastasis.

Note: (The R value is calculated by dividing the ALT by the ALP, using multiples of the ULN for both values. It denotes the relative pattern of ALT and/or ALP elevation is due to cholestatic or hepatocellular liver injury or mixed type injury)

In the absence of cholestasis, these patients should be immediately discontinued from study drug treatment, and repeat LFT testing as soon as possible, preferably within 48 hours from the awareness of the abnormal results. The evaluation should include laboratory tests, detailed history, physical assessment and the possibility of liver metastasis or new liver lesions, obstructions/compressions, etc.

Hepatic toxicity monitoring includes the following LFTs: albumin, ALT, AST, total bilirubin, direct and indirect bilirubin, alkaline phosphatase (fractionated if alkaline phosphatase is grade 2 or higher), creatine kinase, prothrombin time (PT)/INR and GGT. For patients with Gilbert Syndrome: total and direct bilirubin must be monitored, intensified monitoring applies to changes in direct bilirubin only.

Close observation is recommended in case of AST, ALT, and/or bilirubin increase requiring dose interruption, which involves:

1. Repeating liver enzyme and serum bilirubin tests **two or three times weekly**. Frequency of re-testing can decrease to once a week or less if abnormalities stabilize or return to normal values.
2. Obtaining a more detailed history of current symptoms.

3. Obtaining a more detailed history of prior and/or concurrent diseases, including history of any pre-existing liver conditions or risk factors.
4. Obtaining a history of concomitant drug use (including non-prescription medication, herbal and dietary supplements), alcohol use, recreational drug use, and special diets.
5. Ruling out acute viral hepatitis types A, B, C, D, and E; hepatotropic virus infections (CMV, EBV or HSV); autoimmune or alcoholic hepatitis; NASH; hypoxic/ischemic hepatopathy; and biliary tract disease.
6. Obtaining a history of exposure to environmental chemical agents.
7. Obtaining additional tests to evaluate liver function, as appropriate (e.g., INR, direct bilirubin).
8. Considering gastroenterology or hepatology consultations.
9. Assessing cardiovascular dysfunction of impaired liver oxygenation, including hypotension or right heart failure as possible etiologies for liver dysfunction.
10. Liver biopsy as clinically indicated to assess pathological change and degree of potential liver injury.

All cases confirmed on repeat testing meeting the laboratory criteria defined above, with no other alternative cause for LFT abnormalities identified, should be considered as “medically significant”, thus met the definition of SAE (Section 11.2), and reported as SAE using the term “potential drug-induced liver injury”. All events should be followed up with the outcome clearly documented.

Exemestane

The most frequently reported adverse effects for exemestane are gastrointestinal disturbances, hot flashes, arthralgia, myalgia, sweating, fatigue and dizziness. Other reported effects include headache, insomnia, somnolence, depression, skin rashes, alopecia, asthenia and leg oedema. Thrombocytopenia and leucopenia have been reported occasionally. Reductions in bone mineral density can occur with long-term use of exemestane (Cheung et al. 2012). Refer to the package insert of the local supply of exemestane for more details.

Letrozole

The most frequently reported adverse effects for letrozole are hot flashes, night sweats, arthralgia, myalgia vaginal dryness, asthenia. Other reported effects include depression, headache, dizziness, gastrointestinal disturbances, alopecia, skin rash osteoporosis, peripheral edema. Leucopenia, cataract, vaginal bleedings and insomnia have been occasionally reported. Refer to the package insert of the local supply of letrozole for more details.

Anastrozole

The most frequently reported adverse effects for anastrozole are hot flashes, night sweats. Other reported effects include arthralgia, myalgia vaginal dryness, asthenia, headache, dizziness, gastrointestinal disorders, alopecia, skin rash osteoporosis, peripheral edema. Vaginal bleedings, carpal tunnel syndrome and insomnia, have been reported occasionally. Refer to the package insert of the local supply of anastrozole for more details.

Tamoxifen

The most frequently reported adverse effects for tamoxifen are hot flashes, night sweats, vaginal discharge. Other reported effects include Thromboembolic events, ischemic cerebrovascular events, head ache, dizziness, skin rash, peripheral edema, gastrointestinal disorders, cataract, retinopathy, occasionally endometrial cancer and ovarian cysts, neutropenia and thrombocytopenia. Refer to the package insert of the local supply of tamoxifen for more details.

Fulvestrant

The most common clinically significant adverse reactions occurring in $\geq 5\%$ of patients receiving fulvestrant 5 mg were: injection site reactions, nausea, bone pain, arthralgia, headache, back pain, fatigue, pain in extremity, hot flash, vomiting, anorexia, asthenia, musculoskeletal pain, cough, dyspnea and constipation. Pooled safety analysis (SmPC) identified Aspartate Aminotransferase (AST), Alanine Aminotransferase (ALT) or alkaline phosphatase increases in approximately 15% of the treatment population with grade 3 increases seen in 1-2%. There was no difference in rates of AST, ALT and AP elevations between groups treated with 250 mg and 500 mg doses. Please refer to the SmPC for further pooled safety data for multiple fulvestrant 500 mg trials data.

8.4 Treatment with Eribulin

8.4.1 Drug Dispense, Administration and Treatment Regimens

8.4.1.1 Investigational drugs

The investigational drug used in the course of this trial is commercially available eribulin.

The investigator will prescribe eribulin according to the label. Any change of label will be communicated. The IMP Eribulin for all other patients not covered by the label will be provided by Eisai to the participating sites in the study setting and will be administrated as i.v. injection at the study site.

8.4.1.2 Treatment arms

This is a non-randomized Phase II study.

8.4.1.3 Treatment assignment

All hormone-receptor positive, HER2-negative patients with indication to chemotherapy and all triple-negative patients will be assigned to treatment with eribulin.

8.4.1.4 Dispensing the study drug

The investigator will prescribe eribulin according to the label. Any change of label will be communicated. The IMP Eribulin for all other patients not covered by the label will be provided by Eisai to the participating sites in the study setting and will be administrated as i.v. injection at the study site. All dosages given to the patient and all dose changes during the study must be recorded on the Dosage Administration Record CRF.

Eribulin is a cytotoxic anticancer medicinal product and, as with other toxic compounds, caution should be exercised in its handling. Eribulin should be administered in units specialised in the administration of cytotoxic chemotherapy and only under the supervision of a qualified physician experienced in the appropriate use of cytotoxic medicinal products. The use of gloves, goggles, and protective clothing is recommended. If the skin comes into contact with the solution it should be washed immediately and thoroughly with soap and water. If it contacts mucous membranes, the membranes should be flushed thoroughly with water. Eribulin should only be prepared and administered by personnel appropriately trained in handling of cytotoxic agents. Pregnant staff should not handle Eribulin. Using aseptic technique Eribulin can be diluted up to 100 ml with sodium chloride 9 mg/ml (0.9%) solution for injection. It must not be mixed with other medicinal products and should not be diluted in glucose 5% infusion solution. Any unused medicinal product or waste material should be disposed of in accordance with local requirements.

8.4.1.5 Study drug compliance

The investigator and/or study personnel will assess compliance at each patient visit. To accurately determine the patient's drug exposure throughout the study, the following information must be reported on the Drug Administration Record CRF pages for eribulin and in the source document.

- Planned dose administration
- Actual total daily dose administered
- Start and end date of drug administration
- Dose change (no or yes)
- Reason for dose change (e.g. adverse event, dosing error, lab test abnormality etc.)

8.4.1.6 Patient Compliance

Not applicable.

8.4.1.7 Study drug accountability

The investigator or designee must maintain an accurate record of the shipment and dispensing of only for study drugs supplied by Eisai in a drug accountability log (please refer to section 3.4.). The field monitor will note drug accountability during site visits and at the completion of the study. Patients will be asked to return all unused Eisai-supplied study drugs and packaging on an ongoing basis or at the time of study drug discontinuation.

8.4.1.8 Disposal and destruction

The drug supply can be destroyed at the local site. Destruction must be recorded in the local Drug Accountability Log, and will be controlled by the field monitor.

8.4.1.9 Instructions for use of study drug

Patients will receive cycles of 1.23 mg/m² eribulin on days 1 and 8 of a 21-day cycle for 12 months or until disease progression, unacceptable toxic effects, patient or physician request for discontinuation, or serious protocol non-compliance. Eribulin as the ready to use solution is administered intravenously over 2 to 5 minutes. In the EU the recommended dose refers to the base of the active substance (eribulin). Calculation of the individual dose to be administered to a patient must be based on the strength of the ready to use solution that contains 0.44 mg/ml eribulin.

Monitoring of complete blood counts should be performed on all patients prior to each dose of eribulin. Treatment with eribulin should only be initiated in patients with ANC values \geq 1500/ μ l and platelets $>$ 100000/ μ l. The dose reduction recommendations shown below are also shown as the dose of eribulin to be administered based on the strength of the ready to use solution.

Method of administration

The dose may be diluted in up to 100 ml of sodium chloride 9 mg/ml (0.9%) solution for injection. It should not be diluted in glucose 5% infusion solution. Good peripheral venous access, or a patent central line, should be ensured prior to administration. There is no evidence that eribulin mesilate is a vesicant or an irritant. In the event of extravasation, treatment should be symptomatic.

Women of childbearing potential must be advised to avoid becoming pregnant during and up to 3 months after treatment.

All dosages prescribed and dispensed to the patient and all dose changes during the study must be recorded on the Dosage Administration Record CRF.

8.4.2 Dose Adjustments

In General

Doses may be held or reduced for hematologic and other adverse events (see section 8.3.2.1). Dose adjustments are to be made according to the system showing the greatest degree of toxicity. Once dose is reduced due to adverse events, patients should not be re-challenged to a higher dose level.

Dose reductions and delays of treatment should follow general GCP criteria for the application of antineoplastic drugs (Repetto et al. 2003, NCCN-Guidelines) and should be made according to the SPC and/or investigator's brochure. The latest versions of the SPCs ("Fachinformation" according to German Drug Law) of the standard therapy will be provided on the DETECT IV website or by contact the DETECT Study Office in Ulm (Univeritäts-frauenklinik Ulm, Studienzentrale, [name], [name], [contact], [contact], Email: [contact]).

The antineoplastic treatment of a patient can be postponed for up to 4 weeks to allow resolution of toxicity. The investigator must consult the DETECT IV Study Office prior continuing therapy for any patient requiring a delay of study treatment of more than two weeks for any reason.

All patients who require permanent discontinuation of eribulin will be withdrawn from the treatment intervention schedule (start of the 2-year follow-up period).

8.4.2.1 Permitted study drug dose adjustments and interruptions

Treatment with eribulin should continue as long as clinical benefit is observed or until unacceptable toxicity occurs. Management of severe and/or intolerable suspected adverse events may require temporary dose reduction and/or interruption.

For patients who do not tolerate the protocol-specified eribulin dosing schedule, dose adjustments are permitted in order to allow the patient to continue the study. The following guidelines need to be applied: Dose adjustments are permitted for any adverse event suspected to be related to eribulin in those patients unable to tolerate the normal dose. If administration of eribulin must be interrupted because of unacceptable toxicity, eribulin dosing will be interrupted or modified according to the guidelines in TABLE 15 below.

All study drug interruptions or dose modifications must be recorded on the Dosage Administration Record page of the eCRF.

For patients who are unable to tolerate the protocol-specified dosing scheme, dose adjustments and interruptions are permitted in order to keep the patient on the study drugs. The following guidelines should be followed.

The administration of eribulin should be delayed on Day 1 or Day 8 for any of the following:

- Absolute neutrophil count (ANC) < 1000/μl
- Platelets < 75000/μl
- Grade 3 or 4 non-hematological toxicities.

Patients who interrupt eribulin therapy for more than 4 weeks must be discontinued from the study.

Dose reduction during therapy

Dose reduction recommendations for retreatment are shown in the following TABLE 24.

Adverse reaction after previous eribulin administration	Recommended dose of eribulin
Haematological:	
ANC < 0.5 x 10 ⁹ /l lasting more than 7 days	0.97 mg/m²
ANC < 1 x 10 ⁹ /l neutropenia complicated by fever or infection	
Platelets < 25 x 10 ⁹ /l thrombocytopenia	
Platelets < 50 x 10 ⁹ /l thrombocytopenia complicated by haemorrhage or requiring blood or platelet transfusion	
Non-haematological:	
Any Grade 3 or 4 in the previous cycle	
Reoccurrence of any haematological or non-haematological adverse reactions as specified above:	
Despite reduction to 0.97 mg/ m ²	0,62 mg/m²
Despite reduction to 0.62 mg/m ²	Consider discontinuation

Table 24: Eribulin dose modification guidelines for toxicities.

Do not re-escalate the eribulin dose after it has been reduced.

Patients with hepatic impairment

Impaired liver function due to metastases:

The recommended dose of eribulin in patients with mild hepatic impairment (Child-Pugh A) is 0.97 mg/m² administered intravenously over 2 to 5 minutes on Days 1 and 8 of a 21-day cycle. The recommended dose of eribulin in patients with moderate hepatic impairment (Child-Pugh B) is 0.62 mg/m² administered intravenously over 2 to 5 minutes on Days 1 and 8 of a 21-day cycle.

Severe hepatic impairment (Child-Pugh C) has not been studied but it is expected that a more marked dose reduction is needed if eribulin is used in these patients.

Impaired liver function due to cirrhosis:

This patient group has not been studied. The doses above may be used in mild and moderate impairment but close monitoring is advised as the doses may need readjustment.

Patients with renal impairment

Patients with severely impaired renal function (creatinine clearance <40 ml/min) may need a reduction of the dose (see section 3.3.7). The optimal dose for this patient groups remains to be established.

Caution and close safety monitoring as advised. No specific dose adjustments are recommended for patients with mild to moderate renal impairment.

Elderly patients

No specific dose adjustments are recommended based on the age of the patient.

These changes must be recorded on the Dosage Administration Record eCRF.

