Other toxicities	
Grade 1: It toxicity is tolerable, no dose adjustment required.
 
Grade 2: It toxicity is tolerable, no dose adjustment required. It toxicity becomes intolerable, interrupt everolimus until resolution to \leq grade 1. Restart at the same dose. If toxicity recurs at grade 2, interrupt dose until recovery to grade \leq 1. Restart at a lower dose.
 
Grade 3: Interrupt everolimus until recovery to grade \leq1. Reintroduce everolimus at the next lower dose level
 
Grade 4 Discontinue everolimus treatment

Toxicity requiring interruption for >4 weeks	Permanently discontinue treatment.

No specific dose adjustments are recommended for Grade 1 toxicity. However, physicians should always manage patients according to their medical judgment based on the particular clinical circumstances.

Table 15: Everolimus dose modification guidelines for non-hematologic toxicities

Toxicity	Actions
Thrombocytopenia	
 $\geq 75000/\text{mm}^3$: No change
Platelet count	
 $50000/\text{mm}^3$ to $75000/\text{mm}^3$ Hold everolimus treatment until recovery to $\geq 75000/\text{mm}^3$ Reintroduce everolimus at the same dose level $< 50000/\text{mm}^3$ Hold everolimus treatment until recovery to $\geq 75000/\text{mm}^3$ Reintroduce everolimus at the next lower dose level, if available.
Absolute Neutrophil count (ANC)	
 $\geq 1000/\text{mm}^3$: No change $500/\text{mm}^3$ to $1000/\text{mm}^3$ Hold everolimus treatment until recovery to $\geq 1000/\text{mm}^3$ Reintroduce everolimus at the same dose level $< 500/\text{mm}^3$ Hold until recovery to $\geq 1000/\text{mm}^3$. Reintroduce everolimus (at the next lowest dose level, if available).
Febrile neutropenia	Hold further dosing until ANC $\geq 1250/\text{mm}^3$ and no fever. Then resume dosing at the next lower dose level, if available.
Toxicity requiring interruption for > 4 weeks	Permanently discontinue everolimus treatment

Physicians should always manage patients according to their medical judgment based on the particular clinical circumstances.

Table 16: Everolimus dose modification guidelines for hematologic toxicities

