8.3.2.1 Permitted study drug dose adjustments and interruptions

For patients who are unable to tolerate the protocol-specified dosing scheme, dose adjustments and interruptions are permitted in order to keep the patient on the study drugs. The following guidelines should be followed.

These changes must be recorded on the Dosage Administration Record eCRF.

Treatment with ribociclib and standard endocrine therapy should continue as long as clinical benefit is observed or until unacceptable toxicity occurs. Management of severe and/or intolerable suspected adverse events may require temporary dose reduction and/or interruption.

For patients who do not tolerate the protocol-specified ribociclib dosing schedule, dose adjustments are permitted in order to allow the patient to continue the study. The following guidelines need to be applied:

All study drug interruptions or dose modifications must be recorded on the Dosage Administration Record page of the eCRF.

	Dose	Number of tablets & strength
Starting dose	600 mg/d	3 x 200 mg tablets
First Dose reduction	400 mg/d	2 x 200 mg tablets
Second dose reduction	200 mg/d	1 x 200 mg tablets

Table 19: Ribociclib Dose Modification guidelines

If a patient has already decreased ribociclib intake to 200 mg every other day, no further dose reduction is permitted. Patients requiring an additional ribociclib dose reduction will be required to discontinue study treatment.

Patients who interrupt ribociclib therapy for more than 4 weeks must be discontinued from the study.

TABLE 20, TABLE 21, TABLE 22 and TABLE 23 provide the procedure to be followed for ribociclib dose modification in the event of toxicities suspected to be related to the ribociclib treatment. Included are also instructions for re-initiation of ribociclib dosing once sufficient recovery of toxicity is seen.

Toxicity	Actions
HEPATOTOXICITY (BILIRUBIN; SGPT/ALT, SGOT/AST)	

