Thrombocytopenia		
 Grade 1 ($\geq 75 \times 10^9$): No change
Platelet count		
 Grade 2 ($50 \times 10^9 - 75 \times 10^9$) Dose interruption until recovery to grade ≤ 1 Reintroduce ribociclib at the same dose level Grade 3 ($25 \times 10^9 - 50 \times 10^9$) Dose interruption until recovery to grade ≤ 1 Reintroduce ribociclib at the same dose level If toxicity recurs at grade 3: temporary dose interruption until recovery to grade ≤ 1 and reduce ribociclib to the next lowest dose level. Grade 4 ($<25 \times 10^9$) Dose interruption until recovery to grade ≤ 1 Reintroduce ribociclib at the next lower dose level. If toxicity recurs at grade 4: discontinue ribociclib.
Absolute Neutrophil count (ANC)	Neutrophil count	
 Grade 1 ($\geq 1,5 \times 10^9$): No change Grade 2 ($1,5 \times 10^9 - 10^9$): No change Grade 3 ($0,5 \times 10^9 - 1 \times 10^9$): Dose interruption until recovery to $\geq 1.0 \times 10^9/L$ Reintroduce ribociclib at the same dose level. If toxicity recurs at grade 3: temporary dose interruption until recovery to $\geq 1.0 \times 10^9/L$ If resolved in ≤ 7 days, then maintain dose level. If resolved in > 7 days, then reduce ribociclib dose to the next lower dose level. Grade 4 ($<0,5 \times 10^9$): Dose interruption until recovery to $\geq 1.0 \times 10^9/L$ Reintroduce ribociclib at the next lower dose level. If toxicity recurs at grade 4: temporary dose interruption until recovery to $\geq 1.0 \times 10^9/L$ And reduce ribociclib at the next lower dose level.
Febrile neutropenia		
 Grade 3 (ANC $< 1.0 \times 10^9/L$ with a single temperature of $> 38.3^\circ C$ or a sustained temperature of $\geq 38^\circ$ for more than one hour): Dose interruption until improvement of ANC $\geq 1.0 \times 10^9/L$ and no fever. Restart at the next lower dose level. If febrile neutropenia recurs, discontinue ribociclib. Grade 4 (Life-threatening consequences; urgent intervention indicated): Discontinue ribociclib.
Anemia (Hemoglobin)		
 Grade 1 ($\geq 10.0 \times LLN$ g/dl): No change Grade 2 ($\geq 8.0 - < 10 \times LLN$ g/dl): No change Grade 3 ($< 8.0 \times LLN$ g/dl):

Dose interruption until recovery to grade ≤ 2 .

Reintroduce ribociclib at the same dose.

• **Grade 4 (Life-threatening consequences; urgent intervention indicated):**

Discontinue ribociclib

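### Two cross-references in the eribulin dosing text point to other drugs' rules: 8.4.2.1 cites Table 15 (everolimus) and 8.4.2 cites section 8.3.2.1 (ribociclib)

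*Protocol*

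**What the plan says.** Section 8.4 governs eribulin. Its general paragraph in 8.4.2 reads "Doses may be held or reduced for hematologic and other adverse events (see section 8.3.2.1". Section 8.3.2.1 belongs to 8.3, Treatment with Ribociclib. Its tables "provide the procedure to be followed for ribociclib dose modification in the event of toxicities suspected to be related to the ribociclib treatment".

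Section 8.4.2.1 then states that, if eribulin has to be interrupted for unacceptable toxicity, "eribulin dosing will be interrupted or modified according to the guidelines in TABLE 15 below". The table with that number is in the everolimus section, 8.2.2.1, and is captioned "Table 15: Everolimus dose modification guidelines for non-hematologic toxicities".

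The eribulin rules themselves are further down in 8.4.2.1. They consist of the Day 1/Day 8 delay criteria (ANC below 1000/µl, platelets below 75000/µl, or Grade 3 or 4 non-haematological toxicity) and Table 24, which reduces to 0.97 mg/m², then to 0.62 mg/m², then advises considering discontinuation. The same section introduces Table 24 by its correct number for dose reduction at retreatment. Section 8.4.3.1 adds a rule for neuropathy.

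**The concern.** Both pointers are in current dosing text for a cytotoxic drug, and the one in 8.4.2.1 is worded as mandatory. An investigator who follows the printed reference reaches rules written for a different drug, and for some events those rules require something different from Table 24. In some cases the other drug's rule is stricter and would stop or cut eribulin where the eribulin rule would not. In others it is less protective and would keep the full dose where the eribulin rule reduces it. Table 15 also covers only non-haematological toxicity, so the sentence on eribulin interruption cites a table without a neutrophil rule, although section 8.4.3 lists Grade 3/4 neutropenia at 48.3%.

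**Working it through.** No sample size, power or error rate is involved. The check is to trace each reference to what now carries that number, and then to compare the rules.

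**Tracing the two references**
- 8.4.2.1 cites Table 15, which is everolimus, non-haematological (8.2.2.1). The eribulin table is Table 24.
- 8.4.2 cites 8.3.2.1, which is ribociclib: dose steps of 600/400/200 mg in Table 19 and toxicity rules in Tables 20 to 22. The eribulin section is 8.4.2.1.

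**Comparing the rules, if the cited rule is carried over to eribulin**

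| Event | Rule at the cited place | Eribulin rule |
|---|---|---|
| Grade 4 non-haematological toxicity | Table 15, other toxicities: "Grade 4 Discontinue everolimus treatment" | Table 24: 0.97 mg/m² |
| Grade 3 neuropathy | Table 15, other toxicities: resume only at Grade 1 or lower | 8.4.3.1: resume at Grade 0-2, one dose level lower |
| Recurrent febrile neutropenia | Table 21: "If febrile neutropenia recurs, discontinue ribociclib" | Table 24: 0.62 mg/m² if already at 0.97 |
| Recurrent platelets below 25 x 10^9/l | Table 21: "If toxicity recurs at grade 4: discontinue ribociclib" | Table 24: 0.62 mg/m² if already at 0.97 |
| Uncomplicated ANC below 0.5 x 10^9/l for 7 days or less | Table 21: restart one level lower | Table 24: no reduction |
| First platelets 25-50 x 10^9/l with haemorrhage or transfusion | Table 21: restart at the same dose | Table 24: 0.97 mg/m² |
| First ANC 0.5-1.0 x 10^9/l with infection but no fever | Table 21: restart at the same dose | Table 24: 0.97 mg/m² |

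In the first five rows the cited rule is stricter than the eribulin rule. In the last two it is less protective.

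These rows are examples, not a complete count. The same tables also differ for a first Grade 4 febrile neutropenia (Table 21 discontinues, Table 24 gives 0.97 mg/m²), for Grade 2 stomatitis (Table 15 interrupts, whereas the eribulin delay list starts at Grade 3) and for low haemoglobin (Table 21 has an interruption rule, the eribulin delay list has none). Section 8.3.2.1 further contains hepatic and QTc tables.

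**Other stale pointers in the eribulin text**
- 3.4.6 sends severe neutropenia and thrombocytopenia to 8.3.2 (ribociclib) and severe neurotoxicity to 8.2.2 (everolimus).
- The renal paragraph of 8.4.2.1 cites 3.3.7, which is ribociclib pharmacodynamics.
- 8.1 cites 8.3 for eribulin treatment.
- 13.1.1 lists tables for the everolimus and ribociclib cohorts but none for eribulin.

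**The case against.** The strongest reply is that the wrong references cannot really be carried out. The actions in Table 15 name everolimus, as in "Grade 3: Interrupt everolimus until recovery to grade", and its dose levels are milligrams daily or every other day. The tables in 8.3.2.1 name ribociclib and its own steps. A next lower dose level for eribulin exists only in Table 24. The reference in 8.4.2.1 also says that the table is below, which fits Table 24 and not Table 15, and Table 24 is cited by its correct number shortly afterwards. Section 8.4.1.9 refers to the dose reductions shown below. Section 8.4.2 defers to the product information and requires contact with the Study Office before continuing after a delay of more than two weeks.

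All of this stands, and it is why the practical risk is low. It does not make the references correct: both still send the reader of a mandatory dosing instruction to another drug's rules.

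A reader might go further and infer that sites will misdose eribulin, or that a fixed number of event types or patients is affected. The protocol does not support that. It gives no basis for how often a site would apply another drug's table and no recurrence rates, and the differences shown above arise only if the cited rule is carried over.

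**Conclusion.** Both cross-references are wrong as written, in current operative text, and the rules they point to differ from the eribulin rules in substance. This is a minor, wording-only error in safety text. It is not a design choice: nothing suggests that anyone intended eribulin to be dosed under everolimus or ribociclib rules. The eribulin rules are present and correctly labelled in the same section.

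A reader might infer an effect on progression-free survival in the eribulin cohort through dose intensity or early discontinuation. Nothing in the protocol allows that to be shown, and it is not claimed. The size of the point is therefore two wrong operative references, plus the stale pointers of the same kind. The conclusion rests only on the section and table numbers printed in the protocol.

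**What to change.** - In 8.4.2.1, change Table 15 to Table 24.
- In 8.4.2, change 8.3.2.1 to 8.4.2.1.

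In the same amendment:
- In 3.4.6, point both references to 8.4.2.1, adding 8.4.3.1 for neuropathy.
- In the renal paragraph of 8.4.2.1, change 3.3.7 to 3.4.6.
- In 8.1, change 8.3 to 8.4 for eribulin.
- In 13.1.1, name Table 24 for the eribulin cohort.

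The cost is amendment wording only, with no change to design, sample size or analysis.
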